This stage is designed to determine if daily oral ACZ is tolerated and if tachyphylaxis might occur with long-term use for the specific formulation of oral ACZ that we will utilize. Some authors have reported attenuation of the initial increases in CBF with sustained use or oral ACZ though still showing a persistent increase in cerebral perfusion of between 15% - 20%, when compared to pre-treatment levels (Friberg et al., 1990). In this stage, all subjects will receive baseline pCASL and DSC MRI and will start oral ACZ. Patients will continue on 1000 mg BID dose for 24 consecutive weeks and undergo repeat imaging at predetermined intervals. MRI scans and clinical evaluations will be obtained every 6 weeks with contrast-based scans repeated every 12 weeks. Contrast will be administered every 12 weeks to determine DSC measures of blood flow and whether new lesions have formed. As previously stated, DSC provides measurements of not only CBF but also blood volume (CBV) and transit time of blood (MTT). DSC techniques will provide information that cannot be obtained by using pCASL alone that might be important to determine how blood flow is altered with ACZ.

Stage 3 - Many factors contribute to the formation and evolution of lesions in MS (Cotton et al., 2003; Meier and Guttmann, 2006; Narayana et al., 1998). As much as 60% of MS lesions resolve over six

months while the remainder show evidence of persistent damage (Sahraian et al., 2010). In this stage, all subjects will receive baseline pCASL and DSC MRI and will then be randomized to first receive either daily oral therapy with either "**Treatment A**", extended-release ACZ capsules or "**Treatment B**", placebo capsules for 24 consecutive weeks and undergo repeat imaging at predetermined intervals. MRI scans and clinical evaluations will be obtained every 6 weeks with contrast-based scans repeated every 12 weeks. Contrast will be administered every 12 weeks to determine DSC measures of blood flow and whether new lesions have formed and determine how blood flow is altered with ACZ.

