The primary endpoint of this study will be to determine if therapy with oral divided-dose ACZ administered each day for week-long period results in at least 15% increase in CBF. Studies have shown between 10% - 15% decrease in cerebral perfusion in patients with relapsing MS (Adhya et al., 2006). Therefore, increases in CBF of at least 15% might result in change to lesion evolution. Baseline CBF measures will be compared to measures obtained at each dose escalation step using paired *t* test and Mann-Whitney test.

Determine the effect of long-term oral ACZ on lesion evolution. The key secondary endpoint of this study is to determine if long-term use of oral daily divided-dose with ACZ improves tissue integrity in a proportion of MS lesions.

MRI scans will be segmented using into white and gray matter, T2 and T1 lesion components and contrast-enhancing lesion component. Expert raters (I.V., S.D., L.F.), who are blinded to treatment arm (see section 6.1) will perform quality control of the automated segmentation and obtain quantitative measures of cerebral perfusion. The number and volume of T2 hyperintense and T1 hypointense lesion will be determined using MRIAP. The ratio of T1 hypointense/T2 hyperintense lesion will be determined for baseline and each crossover period and correlated with CBF, CBV and MTT measures obtained at similar times using the Spearman rank correlation.

Diffusion tensor imaging (DTI) is a reliable, validated technique that quantitatively measures molecular diffusivity within tissue and provides information about its microstructural integrity. DTI will be used to monitor tissue integrity and correlate change with increases in CBF following ACZ.

Tertiary Objectives

Several studies have quantitated transverse and longitudinal relaxation times within lesions and normal-appearing white matter and gray matter. These studies have shown that changes in both transverse and longitudinal relaxation can precede lesion formation and possibly better evaluate lesion evolution as compared to black hole volumes (Papadopoulos et al., 2010; van Walderveen et al., 1999a; Walsh et al., 2014; Warntjes et al., 2013). We will manually delineate regions of interest within lesions to obtain T2 and T1 relaxometry metrics. Lesions within areas with greatest change in CBF will be compared with those with least change. We anticipate a correlation between relaxometry measures and areas with varying CBF.

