	Day -7 Screen	Wk 0 Visit 1	Wk 2 Visit 2	Wk 4 Visit 3	Wk 6 Visit 4	Wk 8 Visit 6					
Treatment		500 mg PO BID	1000 mg PO BID	1500 mg PO BID	2000 mg PO BID						
H&P	Х	Х	Х	Х	Х	Х					
CBC, CMP	Х					Х					
Urine pregnancy*	Х										
pCASL MRI		Х	Х	Х	Х	Х					
MSFC		Х	Х	Х	Х	Х					
EDSS		Х	Х	Х	Х	Х					
Blood Sample X X X X X X											
* Female participants who have already been evaluated for pregnancy will not be retested unless otherwise indicated											

•												

Stage 2a – Safety/Tolerability & Kinetics of Treatment Effect										
Up to a Total of 10 subjects										
	Wk -4 Screen	Wk 0 Visit 1	Wk 6 Visit 2	Wk 12 Visit 3	Wk 14 Visit 4					
Treatment		1000 mg ACZ BID		d/c ACZ						
H&P	Х	X	Х	Х	Х					
CBC, CMP		X	Х	Х	Х					
Urine pregnancy*		X								
DSC MRI		X		Х						
pCASL MRI		X	X	x	X					
MSFC		X	Х	Х	Х					
EDSS		X	Х	Х	Х					
MFIS, MSWS-12		X	X	x	X					
Blood Sample		X	X	X	X					
* Female pa unless other	rticipants who wise indicated	have already been evaluated	for pregnancy	/ will not be r	retested					

- Additional CBC,CMP will be performed if measured ALT/AST > 1X ULN or if other alterations above baseline

- EDSS Expanded disability status scale
- MSFC Multiple Sclerosis Functional Composite Scale

Stage 2b – Tolerability & Tachyphylaxis of ACZ in MS Subjects									
• Up	to a Tota	I of 10 subjects		-					
	Wk -1 Screen	Wk 0 Visit 1	Wk 6 Visit 2	Wk 12 Visit 3	Wk 18 Visit 4	Wk 24 Visit 5			
Treatment		ACZ at dose identified in Stage 1b							
H&P	Х	X	X	Х	Х	Х			
CBC, CMP		Х	Х	Х	Х	Х			
Urine		Х							
pregnancy*									
DSC MRI		Х		Х		Х			
pCASL MRI		X	Х	X	x	Х			
MSFC		Х	Х	Х	Х	Х			
EDSS		Х	Х	Х	Х	Х			
MFIS, MSWS-12		X	Х	Х	х	Х			
Blood Sample		X	Х	Х	X	X			
* Female pa otherwise in	rticipants v dicated	who have already been evaluat	ed for pregna	ncy will not b	be retested u	nless			

- Additional CBC,CMP will be performed if measured ALT/AST > 1X ULN or if other alterations above baseline
- EDSS Expanded disability status scale
- MSFC Multiple Sclerosis Functional Composite Scale

Stage 3 – F	RCT; Lor	ng-term ther	apy wit	h ACZ	in MS S	Subject	S				
Del	layed-sta	rt design with	n oral th	erapy "	'Treatm	ent A"	(ACZ) o	or "Trea	tment l	B" (placebo)
 Tot 	al of 60 s	subjects									
	Wk -1 Screen	Wk 0 Visit 1	Wk 6 Visit 2	Wk 12 Visit 3	Wk 18 Visit 4	Wk 24 Visit 5	Wk 30 Visit 7	Wk 36 Visit 8	Wk 42 Visit 9	Wk 48 Visit 10	Wk 50 Visit 11
Treatment		Randomize to ACZ or placebo								d/c treatment	End Study
H&P	Х	Х	Х	Х	Х	Х	Х	Х	Х	Х	

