Subjects will receive 1 gram bolus of IV ACZ and a second scan using pCASL sequences will be obtained within 15 minutes of infusion. Subjects will remain in the MRI gantry and receive a third scan to determine CBF at 30 minutes from time of infusion. Subjects will then be removed from the MRI gantry and allowed a break.

Subjects will again be placed on the MRI gantry and scout, 3DT1 and pCASL sequences obtained within 120 minutes from time of ACZ infusion. Subjects will then be removed from the MRI gantry and allowed a break. A final scan will be performed using the same sequences within 240 minutes from time of ACZ infusion.

Stage 1b:

Screening Visit – Subjects will receive a complete medical and neurological examination. In addition, all subjects will obtain CBC, CMP and, if female, urine pregnancy test.

Visit 1 – Subjects will receive non-contrast MRI brain using sequences previously described to ensure proper orientation and registration (scout, 3DT1), sequences necessary for segmentation using MRIAP (2D dual echo, 2D fluid-attenuated inversion recovery [FLAIR]) and pCASL sequences to determine CBF at baseline. Subjects will begin taking 250 mg oral ACZ twice daily and continue for two weeks. Subjects will be encouraged to call the PI with any adverse events (see sections 2.4b and 7.1.2) while on study drug.

Visit 2 – Prior to dose-escalation, subjects will receive non-contrast MRI brain sequences as described above to measure effect of previous oral daily divided dose of ACZ on CBF. Upon completion of MRI, subjects will begin taking 500 mg oral ACZ twice daily and continue for two weeks. Subjects will be encouraged to call the PI with any adverse events (see sections 2.4b and 7.1.2) while on study drug.

Visit 3 – Prior to dose-escalation, subjects will receive non-contrast MRI brain sequences as described above to measure effect of previous oral daily divided dose of ACZ on CBF. Upon completion of MRI, subjects will begin taking 1000 mg oral ACZ twice daily and continue for two weeks. Subjects will be encouraged to call the PI with any adverse events (see sections 2.4b and 7.1.2) while on study drug.

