Visit 4 – Prior to dose-escalation, subjects will receive non-contrast MRI brain sequences as described above to measure effect of previous oral daily divided dose of ACZ on CBF. Upon completion of MRI, subjects will begin taking 1500 mg oral ACZ twice daily and continue for two weeks. Subjects will be encouraged to call the PI with any adverse events (see sections 2.4b and 7.1.2) while on study drug.

Visit 5 – Prior to dose-escalation, subjects will receive non-contrast MRI brain sequences as described above to measure effect of previous oral daily divided dose of ACZ on CBF. Upon completion of MRI, subjects will begin taking 2000 mg oral ACZ twice daily and continue for two weeks. Subjects will be encouraged to call the PI with any adverse events (see sections 2.4b and 7.1.2) while on study drug.

Visit 6 – Subjects will receive non-contrast MRI brain sequences as described above to measure effect of previous oral daily divided dose of ACZ on CBF. Upon completion of MRI, subjects will discontinue use of ACZ.

Stage 2a:

c)

Screening Visit – Subjects will receive a complete medical and neurological examination and obtain screening EDSS evaluation. In addition, all subjects will obtain CBC, CMP and, if female, urine pregnancy test.

Visit 1 – Subjects will receive MRI brain with and without gadolinium contrast utilizing the following sequences in the order listed:

Scout and 3D T1-weighted images to ensure proper orientation and registration 2D dual echo, 3D FLAIR necessary for segmentation

Muti-shell DWI (DTI sequences)

A single shot 2D echo-planar imaging (EPI) for pCASL-based measures of CBF

2D T1-weighted images prior to Gd administration

DSC sequence for measures of CBF, CBV, MTT

2D T1-weighted images after Gd administration

In addition to segmenting MS lesion (T2 hyperintense), we are able to segment T1 pre- and post-Gd lesion volumes. Images obtained at the site at UT are routinely subject to review by a radiologist who is not further involved in image analysis.

Visit 2 – Subjects will receive a complete medical and neurological examination, MSFC & EDSS evaluation as well as patient-reported clinical disability measures (MFIS & MSWS-12) and will be asked questions to ascertain tolerability to daily therapy. All subjects will obtain MRI brain without gadolinium contrast utilizing the sequences described above except for DSC sequence.

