In those unusual instances where adequate control is not obtained by the twice-a-day administration of acetazolamide extended-release capsules, the desired control may be established by means of acetazolamide (tablets or parenteral). Use tablets or parenteral in accordance with the more frequent dosage schedules recommended for these dosage forms, such as 250 mg every four hours, or an initial dose of 500 mg followed by 250 mg or 125 mg every four hours, depending on the case in question.

Acute Mountain Sickness:

Dosage is 500 mg to 1000 mg daily, in divided doses using tablets or extended-release capsules as appropriate. In circumstances of rapid ascent, such as in rescue or military operations, the higher dose level of 1000 mg is recommended. It is preferable to initiate dosing 24 to 48 hours before ascent and to continue for 48 hours while at high altitude, or longer as necessary to control symptoms.

HOW SUPPLIED

Acetazolamide Extended-Release Capsules, 500 mg are white to off-white pellets filled in empty hard gelatin capsules with orange opaque cap imprinted with "EP" in black ink and white opaque body imprinted with "107" in black ink and are supplied as follows:

Unit dose packages of 30 (3x10) NDC 68084-401-21

Storage and Drug Accountability

Acetazolamide tablets will be stored at room temperature (between 68°F to 77°F) as suggested by the manufacturer. Intravenous formulation of ACZ will be stored as lyophilized powder at the temperature specified above in the Hermann Research pharmacy. Lyophilized powder will be reconstituted prior to infusion by the pharmacy. All study medication will be stored at the Hermann Research pharmacy and dispensed as needed during study.

TREATMENT

Rationale for Selection of Dose

The ACZ challenge test, using 1000 mg IV ACZ, is a commonly utilized clinical tool in evaluating patients with chronic intracerebral occlusive disease and is a reliable predictor of critically reduced cerebral perfusion (Vagal et al., 2009). Oral doses as high as 4000 mg daily have been previously used in the NORDIC clinical trial (NORDIC Idiopathic Intracranial Hypertension Study Group Writing Committee et al., 2014).

Participants in this study will be treated with the highest tolerated dose of oral ACZ extended release capsules shown to exert the greatest effect on cerebral perfusion. This dose will also be utilized for an anticipated subsequent large phase 3 trial to determine clinical efficacy.

Study Drug Formulations

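### Stage 1b carries two incompatible dosing ladders: four steps from 500 mg twice daily in the schedule, five steps from 250 mg twice daily in the visit instructions

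*Combined protocol and SAP*

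**What the plan says.** Three parts of the combined protocol set the Stage 1b doses.

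- **Trial Schedule, Stage 1b table.** 500, 1000, 1500 and 2000 mg twice daily, starting at weeks 0, 2, 4 and 6. The last column is week 8. It is labelled Visit 6, although the column before it is Visit 4.
- **Study Design, Stage 1b scheme.** The same four doses at the same weeks, ending at week 8. The text beside it gives 2.5 months per subject for treatment and data collection.
- **Study Visits and Procedures, Stage 1b.** Visit 1: "Subjects will begin taking 250 mg oral ACZ twice daily and continue for two weeks". Visits 2, 3 and 4 move to 500, 1000 and 1500 mg twice daily for two weeks each. At Visit 5, "subjects will begin taking 2000 mg oral ACZ twice daily and continue for two weeks". At Visit 6, "Upon completion of MRI, subjects will discontinue use of ACZ".

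The ceiling is also stated inconsistently. Rationale for Doses Selected gives 1500 mg per day for Stage 1b; Rationale for Study Design and Study Design both give 4000 mg per day.

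The analysis of this stage is described under Primary & Key Secondary Objective: "Baseline CBF measures will be compared to measures obtained at each dose escalation step".

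The later stages are mixed on how far they depend on Stage 1b. The Stage 2a table already fixes "1000 mg ACZ BID", and the Stage 2b rationale says "Patients will continue on 1000 mg BID dose for 24 consecutive weeks". The Stage 2b table, however, says "ACZ at dose identified in Stage 1b", and Rationale for Selection of Dose says "Participants in this study will be treated with the highest tolerated dose of oral ACZ extended release capsules", chosen for the greatest perfusion effect.

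**The concern.** These are operative dosing instructions in current text, and no sentence reconciles them or ranks one above another. A site working from the table and a site working from the visit text would start subjects on different doses, treat them for different lengths of time, and scan them on different doses at the same calendar week.

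Stage 1b exists to measure the change in cerebral blood flow (CBF) at each oral dose and to identify the dose for later work. Its comparison is baseline against each escalation step, so the ladder determines whether there are four or five comparisons and which dose lies behind each visit number. If subjects were handled under different sections, or if scans were labelled by visit or week instead of by dose dispensed, CBF values from different doses would be pooled under one label.

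The on-treatment blood tests are affected too. The table places the only on-treatment CBC and CMP at week 8, labelled Visit 6. Under the visit text, week 8 is when 4000 mg per day begins and Visit 6 comes two weeks later, so the timing of that safety check is also undefined.

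**Working it through.** No sample size, power or significance level is involved. The check is a side-by-side reading plus step arithmetic.

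**Inputs.** Table and scheme: 500, 1000, 1500, 2000 mg twice daily, two weeks each. Visit text: 250, 500, 1000, 1500, 2000 mg twice daily, two weeks each. Screening takes one week (day -7 in the table, week -1 in the scheme). Maximum 10 subjects. The visit text gives no week numbers, so its calendar is inferred from the two-week steps.

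**Stated duration of 2.5 months.** Weeks on drug = 2 × steps; 1 month = 365.25 / 12 / 7 = 4.348 weeks.

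- Four steps: 2 × 4 = 8 weeks; 8 / 4.348 = 1.84 months. With screening, 9 / 4.348 = 2.07 months.
- Five steps: 2 × 5 = 10 weeks; 10 / 4.348 = 2.30 months. With screening, 11 / 4.348 = 2.53 months.

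The stated figure is reproduced only by five steps with the screening week counted. Four steps fall short either way.

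**Dose behind each on-drug scan, by week.**

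| Scan | Table and scheme (mg twice daily) | Visit text (mg twice daily) | Ratio | Difference per day |
|---|---|---|---|---|
| Week 2 | 500 | 250 | 2.0 | 1000 − 500 = 500 mg |
| Week 4 | 1000 | 500 | 2.0 | 2000 − 1000 = 1000 mg |
| Week 6 | 1500 | 1000 | 1.5 | 3000 − 2000 = 1000 mg |
| Week 8 | 2000 | 1500 | 1.33 | 4000 − 3000 = 1000 mg |
| Week 10 | none | 2000 | – | – |

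**Scans.** Table: 1 baseline + 4 = 5 per subject, at most 5 × 10 = 50. Visit text: 1 baseline + 5 = 6 per subject, at most 6 × 10 = 60.

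**Cumulative dose**, as the sum of 2 × dose × 14 days.

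- Table: 14 × (1000 + 2000 + 3000 + 4000) = 140,000 mg = 140 g.
- Visit text: 14 × (500 + 1000 + 2000 + 3000 + 4000) = 147,000 mg = 147 g.

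Total exposure is therefore close. The difference lies in the starting dose, the timing and the scan-to-dose mapping.

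**Ceiling.** Both ladders reach 2 × 2000 = 4000 mg per day, which is 4000 / 1500 = 2.7 times the limit in Rationale for Doses Selected. In the table only the first step (1000 mg per day) lies within that limit. In the visit text only the first two do (500 and 1000 mg per day).

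**Which ladder was intended?** The evidence conflicts.

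- For four steps: the table and scheme agree with each other. Study Design specifies extended-release drug for this stage, and the only oral product described in full is a 500 mg extended-release capsule, so 250 mg is not a whole capsule. Tablets are mentioned under Storage and Drug Accountability and Study Drug Formulations, but without a strength.
- For five steps: the 2.5-month duration, and the table's own Visit 6 label with no Visit 5 before it.

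The document does not settle the question.

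**The case against.** The contradiction itself is hard to dispute. The case on the other side is that it matters little.

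- **Matched by dose instead of by week, the ladders largely agree.** All four table doses appear in the visit text, which only adds a lower step in front. This is correct, and it means a consistently applied ladder of either kind would yield CBF at 500, 1000, 1500 and 2000 mg twice daily.
- **Each scan is already tied to the preceding dose.** The visit text says every scan measures the effect of the previous dose, and Study Design says perfusion is determined for each dose. This stands as long as one ladder is followed throughout, which the document does not secure.
- **No particular hazard is shown.** Both ladders end at the same maximum, and the higher starting dose, 500 mg twice daily, is the recommended glaucoma dose in the package insert. This also stands: the twofold starting difference is a conflict of instructions, not a demonstrated safety risk.
- **Later doses are already written in.** 1000 mg twice daily is a step in both ladders and is fixed for Stage 2a and in the Stage 2b rationale. This limits the downstream effect. It does not remove it, because the Stage 2b table and Rationale for Selection of Dose still refer back to dose finding.
- **Preferring four steps drops the gentlest titration step without a tolerability argument.** This is fair. The investigator has to confirm which ladder is intended.

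These points bear on the size of the problem and the choice of remedy. None of them reconciles the two schedules.

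**Conclusion.** The concern holds. Stage 1b has two dosing schedules that cannot both be followed, plus a third, lower ceiling that neither respects. They differ twofold in starting dose, by 8 against 10 weeks on drug, by 4 against 5 baseline-to-dose comparisons, and in the dose behind the scan at all four shared on-drug weeks. The 10-week figure assumes that the five two-week steps run back to back.

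The reach is limited to an open-label, uncontrolled stage of up to 10 subjects. The Stage 3 primary analysis and sample size in Sample Size and Statistical Methods do not depend on it. This should be fixed, but it does not threaten the trial's main conclusion.

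**What to change.** The investigator should confirm the intended ladder, and every section should then carry that one.

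**Four-step version (simplest).** It already matches the table, the scheme and the 500 mg capsule. Rewrite the Stage 1b visit instructions as:

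- Visit 1, week 0: baseline scan, start 500 mg twice daily.
- Visit 2, week 2: scan, then 1000 mg twice daily.
- Visit 3, week 4: scan, then 1500 mg twice daily.
- Visit 4, week 6: scan, then 2000 mg twice daily.
- Visit 5, week 8: final scan, CBC and CMP, stop drug.

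Relabel the table's week 8 column as Visit 5. The cost is a text amendment with no added procedures.

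**Five-step version.** Add to the table and scheme a 250 mg twice daily first step, a week 8 visit (Visit 5) and a week 10 visit (Visit 6, with scan, CBC and CMP), and name the product and strength that deliver 250 mg. Relative to the table, this costs one extra visit and one extra scan per subject, for up to 10 subjects, plus a 250 mg supply.

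**Under either version.**

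- Correct the Stage 1b maximum in Rationale for Doses Selected to 4000 mg per day.
- Align the per-subject duration in Study Design with the chosen ladder, stating whether screening is counted.
- In the CBF-by-dose comparison, label each scan with the dose actually dispensed before it. The documents do not say whether Stage 1b has finished. If it has, this labelling should be done from the dispensing record.
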